Questions regarding patient eligibility, treatment, dose modifications, protocol, IRB, model consent revisions, site regulatory documents, biospecimen collection, requirements, and processing, etc.	AFT Clinical Research Associates Email: [REDACTED]
Questions related to AE/SAE reporting	Novella Clinical: Safety Management Ph: US Toll Free: [REDACTED] Email: [REDACTED]

Synopsis and Study Schema

Study Title	A Phase I Study of Ibrutinib (PCI-32765) in Combination with Revlimid/dexamethasone (Rd) in Relapsed/Refractory Multiple Myeloma
Study Number	AFT-15
Study Type/Phase	Phase Ib
Clinical Indication	Relapsed/Refractory Multiple Myeloma
ClinicalTrials.gov Identifier	NCT03702725
IND Number	140017
Number of Study Patients	19-25 (Dose escalation:9-18; Dose expansion: 4-10)
Estimated Duration of Trial	Approximately 42 to 48 months to enroll *Patients are treated until disease progression
Rationale	In the last decade, significant progress has been made in the treatment of Multiple Myeloma (MM), primarily due to the introduction of proteasome inhibitors (PI) and immunomodulatory drugs (IMiDs). However, nearly all patients ultimately relapse and require further therapy, making the development of new compounds for MM therapy an important priority. Preclinical studies suggest synergism between lenalidomide and ibrutinib in MM. The anti-myeloma effects of lenalidomide have been previously described and include caspase-8-dependent apoptosis of MM cells, inhibition of angiogenesis, and activation of NK and T effector cells. Both ibrutinib and lenalidomide downregulate IRF4, a master transcriptional factor that mediates myeloma cell survival, and both exert effects on the BM microenvironment with overlapping yet distinct targets that influence MM cell growth and survival. The combination of lenalidomide and ibrutinib is thus an attractive therapeutic strategy not only as a potent anti-MM regimen but also in terms of positively impacting bone disease.

Primary Objective	
 1. To determine the maximum tolerated dose (MTD) in phase I and recommended dose in extension cohort of ibrutinib in combination with lenalidomide and dexamethasone 2. To examine the safety profile of ibrutinib in combination with lenalidomide and dexamethasone

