The maximum tolerated dose is defined as the highest dose level among those tested where at most 1 out of 6 patients develops a DLT prior to the start of their second cycle of treatment and the next highest dose level is such that 2 or more out of a maximum of 6 patients treated at this dose level developed a DLT prior to the start of their second cycle of treatment.

Enrollment and determination of MTD

A minimum of 2 or a maximum of 6 patients will be accrued to a given dose level. Doses will not be escalated in any individual patient. If none of the first 3 patients treated at a given dose level develops a DLT during the first cycle of treatment, enrollment to the dose level will be closed and enrollment will reopen at next higher dose level. If there are no other higher dose levels to be tested, three additional patients will be enrolled at the current dose level to confirm MTD. If one of the first 3 patients treated at a given dose level develops a DLT during the first cycle of treatment, three additional patients will enroll onto the current dose level. If, at any time in the enrollment of these 3 additional patients, a patient develops a DLT, enrollment will be closed to this dose level. Enrollment will be re-opened to the next lower dose level if fewer than

6 patients have been treated at that dose level. If none of these 3 additional patients develops a DLT during the first cycle of treatment, enrollment to this dose level will be closed and enrollment will reopen at next higher dose level. If there are no other higher dose levels to be tested, this will be considered the MTD.

For this protocol, the patient must return to their registration institution for evaluation and continuation of treatment (at least every 28 ± 3 days) according to the test schedule. Patients who have not had disease progression and have experienced acceptable toxicity will be eligible to continue protocol retreatment at their current dose level until disease progression, unacceptable toxicity, or refusal. Those patients who have not progressed and who have experienced unacceptable toxicity may be eligible to continue protocol retreatment at a lower dose.

Criteria for discontinuation of all protocol therapy include:

- Tumor progression
- Request by the patient to withdraw
- Unacceptable adverse events
- Treatment delay of >4weeks

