2.4. Endpoints

2.4.1 Primary and Secondary

Primary:

1. Maximum tolerated dose (MTD): The maximum tolerated dose (MTD) is defined as the highest dose level among those under consideration where at most 1 of 6 patients develops a dose limiting toxicity and 2 or more of the 3-6 patients treated at the next higher dose level develop a dose limiting toxicity.
2. Safety profile: The maximum grade of each type of toxicity will be recorded for each patient. For each toxicity reported by dose level, the percentage of patients developing any degree of that toxicity as well as the percentage of patients developing a severe degree (Grade 3 or higher) due to treatment will be determined.

Secondary:

1. Progression free survival (PFS) defined as the time from study entry to the documentation of disease progression using IMWG criteria or death due to any cause.
2. Overall survival (OS) is defined as time from registration to death due to any cause.
3. Overall Response rate(ORR)
4. Duration of response, defined as the time from documented response to disease progression among those patients whose disease meets the IMWG criteria for disease response.
5. Safety Profile: CTCAE v5.0 will be used to grade and assign attribution to each adverse event reported.

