8.3. Criteria for Discontinuation of Protocol treatment

Patients are continued on treatment until any of the criteria for discontinuation of protocol therapy is met, which includes:

- Tumor progression
- Request by the patient to withdraw
- Unacceptable adverse events
- Treatment delay of >4weeks
- Intercurrent illness which would, in the judgment of the investigator, affect assessments of clinical status to a significant degree or require discontinuation of drug

Administration of non-protocol anti-tumor drug during the trial. Patients who discontinue treatment for any of the above reasons will go to survival follow-up where late toxicities and clinical outcome information will be collected every 6 months for a maximum of 2 years post registration. Once a patient has entered the survival follow-up phase of the trial, his/her therapy is at the discretion of the treating physician.

9. Study Assessments and Procedures

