14.3.1 Statement for Secondary Endpoints

Secondary Endpoints include:

Maximum Toxicity Grade:

The maximum grade of each type of toxicity will be recorded for each patient. For each toxicity reported by dose level, the percentage of patients developing any degree of that toxicity as well as the percentage of patients developing a severe degree (Grade 3 or higher) will be determined.

Number/Duration of Response:

For each dose level, the number of response and the duration of response will be tabulated. The duration of response is the time from initiation of first response to first documentation of disease

progression or death. Patients who have not progressed will be censored at the date of their last disease evaluation.

Progression-free Survival (PFS)/ Overall Survival (OS)

Secondary endpoints for the expansion cohort include progression-free survival (PFS) and overall survival (OS) time.

Survival time is defined as the time from study entry to death due to any cause.

Progression-free survival time is the time from study entry to the documentation of disease progression or death due to any cause.

If a patient dies without a recurrence documented, the patient will be censored at the date of last disease evaluation. The distribution of response times, progression-free survival times and survival times will be estimated using the Kaplan-Meier method.

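### Survival follow-up stops 2 years after registration only for patients off treatment, so the Kaplan-Meier OS curve is biased upward beyond month 24 (minor)

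*Combined protocol and SAP*

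**What the plan says.** Section 8.3 sets the follow-up rule for patients off treatment: "Patients who discontinue treatment for any of the above reasons will go to survival follow-up where late toxicities and clinical outcome information will be collected". Its stated frequency and limit are "every 6 months for a maximum of 2 years post registration". The clock runs from registration, not from the end of treatment.

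The same section sets no time limit for patients on treatment: "Patients are continued on treatment until any of the criteria for discontinuation of protocol therapy is met". Section 1.2 gives the condition for continuing as "until disease progression, unacceptable toxicity, or refusal", so stable disease is enough and a response is not required. The synopsis agrees: "Patients are treated until disease progression".

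Section 2.4.1 defines the endpoint without a horizon: "Overall survival (OS) is defined as time from registration to death due to any cause". In section 14.3.1 (Statement for Secondary Endpoints; the number 14.3.1 is used twice) the estimator is given as "progression-free survival times and survival times will be estimated using the Kaplan-Meier method", and the population as "Secondary endpoints for the expansion cohort include progression-free survival (PFS) and overall survival (OS) time". That section gives no OS censoring rule, data cut-off or truncation point. The synopsis and section 1.2 send patients to survival follow-up without stating a duration, and Table 15 has no survival follow-up column.

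**The concern.** Kaplan-Meier needs censoring that is unrelated to prognosis. Up to month 24 that holds here, because section 8.3 follows patients for survival whether or not they are on treatment.

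At month 24 every living off-treatment patient is censored. From then on, only patients still on protocol treatment without progression are at risk. Each of them leaves follow-up on or soon after stopping, most often because of progression, which is when the risk of death rises. Those later deaths are not counted, and the curve is carried by the patients with the best prognosis.

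OS is a named secondary endpoint. What is at stake is a late plateau, or a 36- or 48-month rate, that looks like durable survival but comes from the follow-up rule.

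**Working it through.** **The plan's own time figure.** The plan gives no OS sample size, event count or target rate. The only computed time figure is the enrolment period in section 14.2. Six escalation cohorts × 6 months + 2 months + 4 to 10 expansion patients at 1 per month = 36 + 2 + 4 to 10 = 42 to 48 months, which reproduces it. Early patients can therefore pass month 24 before accrual closes, so data beyond month 24 are plausible.

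**Inputs from the protocol.** Table 1 (lenalidomide plus dexamethasone, first trial): median time to progression 11.1 months, median OS 29.6 months. Section 1.1.1: event-free survival about 5 months; median OS 9 months, extended to over 15 with newer agents.

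**Assumptions not in the documents.** Times are exponential. Treatment stops at progression. A share f = 0, 5% or 15% of the progression-or-death hazard is death on treatment. The 15-month OS figure is paired with 5 months on treatment.

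**Formulas.** Let λ = ln 2 / (median time on treatment), d = fλ, a = λ − d, and h = the death hazard after stopping, solved so that OS at its median is 0.50.

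- True OS: S(t) = exp(−λt) + a[exp(−ht) − exp(−λt)]/(λ − h).
- Kaplan-Meier under section 8.3: equal to S(t) up to month 24. Beyond that only on-treatment patients are at risk and their hazard is d, so in large samples KM(t) = S(24) × exp(−d(t − 24)).

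**One case in full (11.1/29.6, f = 5%).** λ = 0.693/11.1 = 0.06245; d = 0.00312; a = 0.05932; h = 0.04847.

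- S(24) = 0.2234 + 0.05932 × (0.3125 − 0.2234)/0.01398 = 0.601.
- KM(36) = 0.601 × exp(−0.00312 × 12) = 0.579.
- True S(36) = 0.399.

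**All cases at 36 months.**

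| Time on treatment / OS medians | f | S(24) | True OS(36) | KM(36) |
|---|---|---|---|---|
| 11.1 / 29.6 | 0 | 0.605 | 0.395 | 0.605 |
| | 5% | 0.601 | 0.399 | 0.579 |
| | 15% | 0.593 | 0.407 | 0.530 |
| 5 / 15 | 0 | 0.255 | 0.094 | 0.255 |
| | 5% | 0.263 | 0.102 | 0.242 |
| | 15% | 0.281 | 0.123 | 0.219 |
| 5 / 9 | 0 | 0.073 | 0.014 | 0.073 |
| | 5% | 0.075 | 0.015 | 0.069 |
| | 15% | 0.079 | 0.016 | 0.062 |

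Adding other discontinuations at 20% of the hazard moves these values by less than 0.01. A simulation of 400,000 patients per scenario, with those discontinuations and f = 5% or 15%, agrees. If deaths in the month after stopping are also captured, it gives 0.52 to 0.56 at 36 months on the 11.1/29.6 benchmark, still against 0.40 to 0.41.

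**Median.** On 11.1/29.6 the Kaplan-Meier median is 24 + ln(S(24)/0.5)/d. For f = 15% (d = 0.00937) this is 24 + 0.171/0.00937 ≈ 42 months. For f = 5% it is 24 + 0.185/0.00312 ≈ 83 months. For f = 0 it is never reached. The true value is 29.6. At true medians of 9 and 15 months the median falls before month 24 and is unaffected.

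**Patients behind the tail.** Still on treatment at month 24: exp(−0.06245 × 24) = 0.223, or about 2.2 of 10 (0.9 of 4) expansion patients. With the other discontinuations it is 0.166, or 1.7 of 10. With a 5-month median, exp(−0.1386 × 24) = 0.036, or about 0.4 of 10.

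**With one rule for everyone.** In the simulation, following all patients to a common 60 months returns 0.60, 0.40 and 0.26 at 24, 36 and 48 months, matching true OS. Truncating at 24 months also removes the bias.

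**The case against.** The best defence is that the protocol does not settle that follow-up ends when treatment stops. The synopsis has charts reviewed for survival without a cap. Section 10.5.3 mentions follow-up for OS after progression. Section 10.5.1 collects serious adverse events to 90 days after treatment. Sections 10.4 and 10.5.1 have later deaths from progressive disease reported in the database with no stated limit. These soften the effect, and the sponsor may have meant the 2-year limit for everyone. But none of them sets a survival schedule for all patients, and section 8.3 is the only place that gives a duration. Counting late deaths without following the survivors equally would not give a sound curve either.

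The second defence is scale: 4 to 10 expansion patients, no OS hypothesis or decision rule, and no planned 36- or 48-month rate. This stands, and it is why the point is minor.

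A reader might infer more than the documents support:

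- **That any reported median will be too long.** This needs a true median above 24 months. The 29.6-month benchmark comes from patients with 1 to 3 prior therapies, whereas this trial requires progression within 60 days of the last regimen or failure to reach minimal response on it. The 9- and 15-month figures in sections 1.1.1 and 1.1.3 leave the median untouched.
- **That a high chance of an unreached median measures the bias.** With 24-month OS of 0.605, the binomial chance of at most 4 deaths in 10 is 0.646, and of at most 10 in 22 is 0.787. Truncating at month 24 leaves both unchanged.
- **That the curve must go completely flat.** This follows only if nobody dies on treatment.

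**Conclusion.** The point holds for the part of the OS curve after month 24 and nowhere else. Followed as written, section 8.3 makes censoring there depend on treatment status, which is prognostic, and the curve is too high in every scenario examined. At 36 months the overstatement is roughly 0.12 to 0.21 on the 11.1/29.6-month benchmark, 0.10 to 0.16 on 5/15, and about 0.05 to 0.06 on 5/9. These sizes depend on exponential times, the assumed share of on-treatment deaths, and no survival information after treatment stops. Capturing deaths in the serious adverse event window shrinks them but does not remove them. Few patients would be affected, and no decision in the plan depends on late OS. Severity: minor.

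**What to change.** In section 14.3.1 (Statement for Secondary Endpoints), state that OS is censored at 24 months from registration for every patient regardless of treatment status, that the 24-month OS rate is reported with its confidence interval, and that OS is neither plotted nor quoted beyond 24 months. Give the same survival follow-up duration in the synopsis and section 1.2 as in section 8.3.

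This costs one sentence of analysis text and a consistency edit, with no extra data collection. The loss is the few late on-treatment observations, which are the ones that produce the bias. Following every patient to a single later cut-off would also remove it, at the price of longer follow-up; the choice is the sponsor's, provided one rule covers all patients.

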9.1. Assessment Types

9.1.1 Imaging Assessments

A CT/MRI scan will be collected if clinically indicated for all participants at screening (within 14 days prior to registration). A repeat scan will be collected if clinically indicated at completion of cycle 6 for patients with extramedullary disease indicated on the baseline scan.

9.1.1.1 Central Imaging Review

Scans should be submitted to Imaging Core Lab (ICL) at Ohio State University for central review within 3 days of acquisition.

The complete CT scans will be submitted to the Imaging Core Laboratory in digital DICOM format; BMP files, JPG files, or hard copies (films) are not acceptable.

The entire imaging data in DICOM format must be submitted to the ICL within no more than 30 business days once the image acquisition is completed at site.

De-identify the patient data using institutional procedures to remove patient name and medical record number while preserving the patient ID number and protocol number of the AFT trial. The de-identified digital images may be burned to a CD or transferred to a PC based system for further electronic data transfer purposes.

Data can be electronically transferred to the Imaging Core Lab by 1) Web Transfer; 2) FTP transfer:

1. Web Transfer:

Any PCs with internet access and web browser (e.g., Internet Explorer, Mozilla Firefox) can be used to transfer DICOM images and other required files to the ICL through website upload.imagingcorelab.com. The standard Web Transfer information will be provided separately through the specific trial e-mail, per the request by participating sites before their first data submission.

2. FTP Transfer:

Any FTP software can be used to initiate access to the secure FTP Server of the ICL. The standard FTP access information will be provided separately through the specific trial e-mail, per the request by participating sites before their first data submission.

Send an e-mail notification to inform the Imaging Core Lab at the specific trial email of the data submission **once the data transfer is completed**.

3. Shipment/Mail (not preferred but accepted):

If the above electronic data transfers cannot be achieved, the de-identified images in DICOM format can be burned to a CD, labeled with info of patient ID, study date, baseline/follow-ups on the CD cover, and mailed to the ICL at:

Phone: [REDACTED]
Fax: [REDACTED]

Any questions or problems about the data transfer to the Imaging Core Lab, email the ICL at the specific trial email [REDACTED], or call the ICL IT group at [REDACTED] or [REDACTED] for help.

9.1.2 Safety and Tolerability Assessments

Hematology and chemistry assessments (WBC, ANC, Hgb, PLT, SGOT AST, total bilirubin, alkaline phosphatase, creatinine, potassium, sodium albumin) and LDH/Uric acid levels will be reviewed at screening and monitored throughout the study. Patients will visit the clinic monthly for laboratory assessments, physical examination, concomitant medication review, and adverse event assessment. Refer to the study table assessment table in Section 9 for details on study assessments and procedures performed for this trial.

9.1.3 Electrocardiogram

ECG will be performed at screening and at end of study treatment. As there are rare events of arrhythmia/afibrillation associated with ibrutinib, ECGs may also be performed during the course of the study as deemed needed by the investigator.

9.1.4 Biomarkers/Correlative Studies

Bone marrow aspirates will be collected at pre-treatment and end of cycle 1 MicroRNA-profiling.

Peripheral blood will be collected at pretreatment and after cycles 1, 3, and 6 for immunome studies. Refer to Section 13 for detailed correlative studies information.

9.1.5 Follow-up for Other Malignancies

Occurrences of any new malignant tumors including solid tumors, skin malignancies and hematologic malignancies will be reported throughout study participation, including duration of study treatment and during any protocol specified follow-up periods.

Table 15 **Schedule of Assessment**

Treatment Day → Assessments and Procedures ↓	≤ 14 days prior to registration	Day 1 (all cycles)	Day 15 ± 2 days (all cycles)	End of Cycle 1	End of Cycle 3	End of Cycle 6	At end of treatment or treatment discontinuation
History and exam, weight ^a	X	X	X				X
Height	X						
ECOG Performance Status	X	X	X				X
Adverse event assessment	X	X	X				X
Concomitant Medications	X						X
Hematology group: WBC, ANC, ALC, Hgb, and PLT ^b	X	X	X				X
Chemistry group SGOT AST, total bili, Alk Phos, Creatinine, potassium, calcium, magnesium, phosphorus, sodium, albumin), blood glucose ^b	X	X	X				X
TSH, Free T4 ^{cc}	X						
LDH, Uric Acid ^b	X	X	X				X
Serum pregnancy test ^d	X						
Complete body CT	X	X ^e				X ^e	X ^e
Bone Marrow Biopsy ^f	X			X			
Mandatory blood specimens ^g	X	X ^g		X ^g	X ^g	X ^g	
ECG ^h	X						X

Treatment Day → Assessments and Procedures ↓	≤ 14 days prior to registration	Day 1 (all cycles)	Day 15 ± 2 days (all cycles)	End of Cycle 1	End of Cycle 3	End of Cycle 6	At end of treatment or treatment discontinuation
Serum Immunoglobulins, monoclonal protein and free light chain; beta 2 microglobulin ⁱ	X						X

- a. History, exam, and weigh will be done on day 1 of subsequent cycles after cycle 2
- b. Labs will be done weekly for the first 2 cycles, then on day 1 of subsequent cycles
- c. TSH and Free T4 at screening and every 2 cycles
- d. To be performed within 7 days of receiving drug.
- e. If clinically indicated for those with extramedullary disease indicated on baseline CT at completion of cycle 6 (cycle 6 day 28 ±3 days) or to confirm CR
- f. 2 tubes of 5 ml each of bone marrow aspirates in green tube (2) to be collected pre-treatment (prior to start of cycle 1) and at end of cycle 1 (prior to start of cycle 2).
- g. 15 ml peripheral blood to be collected prior to start of treatment and at end of cycles 1, 3, and 6 for the immunome correlate
- h. ECG should be performed within 14 days prior to registration and end of treatment, and as needed during the course of the study.
- i. Immunoglobulins, serum free light chains (kappa and Lambda), serum monoclonal protein, beta 2 microglobulin ≤ 14 days prior to registration and day 1 of each cycle. 24-hour Urine Protein and immunofixation ≤ 14 days prior to registration, and every 3 months.

10. Adverse Events

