3.1. Inclusion Criteria

1. Men and women ≥ 18 years
2. Eastern Cooperative Oncology Group (ECOG) performance status of 0–1 (Appendix I).
3. Symptomatic MM (as defined by revised IMWG criteria) with measurable disease, defined here as having at least one of the following:
 - Serum monoclonal protein ≥ 0.5 g/dL
 - ≥ 200 mg of monoclonal protein in the urine on 24 hour electrophoresis

- Serum immunoglobulin free light chain: involved FLC ≥ 10 mg/dL (≥ 100 mg/L) AND abnormal serum immunoglobulin kappa to lambda free light chain ratio.
- 4. At least 1 prior therapy with demonstrated disease progression following the most recent line of treatment.
- 5. Progression of disease within 60 days of completion of last therapeutic regimen or the failure to achieve minimal response while on last treatment (according to IMWG).
 - Patients should not have progressed on lenalidomide at a dose of more than 10 mg.
- 6. No prior treatment with ibrutinib or any other protein kinase inhibitory drug or drug targeting the BCR signal transduction pathway.
- 7. Patients with prior daratumumab and allogeneic stem cell transplant are included.
- 8. PT/INR $<1.5 \times$ ULN and PTT (aPTT) $<1.5 \times$ ULN, except if on anticoagulation for medical reasons in which case INR should be ≤ 3
- 9. Adequate hematologic function independent of transfusion and growth factor support for at least 7 days prior to registration, with the exception of pegylated G-CSF (pegfilgrastim) and darbopoeitin which require at least 14 days prior to screen and enrollment defined as:
 - Absolute neutrophil count (ANC) $\geq 1000/\text{mm}^3$ independent of growth factor support.
 - Transfusion independent platelet counts $\geq 75,000/\text{mm}^3$ (or $\geq 50,000/\text{mm}^3$ if bone marrow involvement is $\geq 50\%$).
 - Hemoglobin level ≥ 8 g/dL, independent of transfusion support.
- 10. Biochemical values must be within the following limits within 7 days prior to registration
 - Alanine aminotransferase (ALT) and aspartate aminotransferase (AST) $\leq 2.5 \times$ upper limit of normal (ULN).
 - Total bilirubin $\leq 1.5 \times$ ULN (unless bilirubin rise is due to Gilbert's syndrome or of non-hepatic origin).

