6.2. Pre-Treatment Criteria

A treatment may begin on the scheduled Day 1 of a new cycle if:

- The ANC is $\geq 1,000/\mu\text{L}$;
- The platelet count is $\geq 50,000/\mu\text{L}$;
- Any Ibrutinib or lenalidomide-related allergic reaction/hypersensitivity or sinus bradycardia/ other cardiac arrhythmia adverse event that may have occurred has resolved to \leq grade 1 severity;
- Any other Ibrutinib or lenalidomide-related adverse event that may have occurred has resolved to \leq grade 2 severity.

Laboratory values (excluding Child Pugh score) on Cycle 1, Day 1 must meet eligibility criteria per Section 3.1 (Inclusion Criteria).

6.2.1 Cycle 1 Day 1

Cycle 1 Day 1 hematology and chemistry laboratory assessments will be repeated if not performed within 7 days of starting study treatment.

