6.3.1.1 Overdose

There is no specific experience in the management of ibrutinib overdose in patients. No maximum tolerated dose (MTD) was reached in the Phase 1 study in which subjects received up to 12.5 mg/kg/day (1400 mg/day). Healthy subjects were exposed up to single dose of 1680 mg. One healthy subject experienced reversible Grade 4 hepatic enzyme increases (AST and ALT) after a dose of 1680 mg. Subjects who ingested more than the recommended dosage should be closely monitored and given appropriate supportive treatment.

Refer to Section 11 for further information regarding AE reporting.

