7.1. Definition of Dose-Limiting Toxicity (DLT)

Attributions should be made as possibly, probably, or definite.

Table 9 Dose limiting toxicities (DLT)

Toxicity	DLT Definition
Hematologic	Grade 4 thrombocytopenia or Grade 3 thrombocytopenia with bleeding or requirement for platelet transfusion.

	Grade 4 neutropenia lasting more than 5 days.
Other nonhematologic*	≥ grade 3 as per NCI Common Terminology Criteria for Adverse Events (CTCAE) version 5.0*
	Grade 4 febrile neutropenia
	≥ grade 3 hyperglycemia due to dexamethasone if it cannot be controlled with appropriate therapy
	Treatment delays ≥ 21 days for any non-hematologic or hematological toxicity
	Treatment related death
	Grade ≥ 3 thrombotic/embolic events including DVT
	Grade 4 nausea, vomiting and diarrhea

*except grade 3 nausea, vomiting, diarrhea that does not require tube feeding, total parenteral nutrition or prolonged hospitalization, diarrhea responsive to medical treatment, nausea or vomiting controlled with antiemetics, or transient electrolyte abnormalities that resolve < grade 1 within 48 hours

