8.1.2 Dose Modification for Hepatic Impaired Subjects

Ibrutinib is metabolized in the liver and therefore subjects with clinically significant chronic hepatic impairment at the time of screening (Child-Pugh class B or C) are excluded from study participation.

- For subjects with existing chronic mild hepatic impairment (Child-Pugh class A) at enrollment, the starting dose has to be adjusted to a level of 280 mg daily.
- For subjects who develop mild hepatic impairment while on study (Child-Pugh class A), the recommended dose reduction for ibrutinib/placebo is to a level of 280 mg daily.
- For subjects who develop moderate to severe hepatic impairment while on study (Child-Pugh class B and C)
- Study drug will be held until resolved to mild impairment (Child-Pugh class A)

Subjects who develop acute hepatic toxicity with liver enzymes Grade 3 or higher while on study should be managed per standard dose modification guidelines.

Table 12 Dose Modification Guidelines for Hepatic Toxicity

Measure	1 point	2 points	3 points
Total bilirubin, $\mu\text{mol/L}$ (mg/dL)	$<34 (<2)$	34-50 (2-3)	$>50 (>3)$
Serum albumin, g/L (g/dL)	$>35 (>3.5)$	28-35 (2.8-3.5)	$<28 (<2.8)$
PT INR	<1.7	1.71-2.30	>2.30
Ascites	None	Mild	Moderate to Severe
Hepatic encephalopathy	None	Grade I-II (or suppressed with medication)	Grade III-IV (or refractory)

Points	Class
5-6	A
7-9	B

Source:

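### After Cycle 1 Day 1 the schedule requires neither ALT nor INR, although the DLT definition and the on-study hepatic rules can turn on them

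*Combined protocol and SAP*

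**What the plan says.** Two places list the safety laboratory tests. Table 15 gives the chemistry row as "Chemistry group SGOT AST, total bili, Alk Phos, Creatinine, potassium, calcium, magnesium, phosphorus, sodium, albumin), blood glucose". Section 9.1.2 gives "SGOT AST, total bilirubin, alkaline phosphatase, creatinine, potassium, sodium albumin" among its analytes. The lists differ elsewhere (calcium, magnesium, phosphorus and glucose appear only in Table 15), but both have AST as the sole transaminase and neither has PT/INR or aPTT. Footnote b of Table 15 makes the listed tests weekly in the first two cycles and Day 1 thereafter.

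Other sections rely on the unlisted tests:

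- **Eligibility (Section 3.1).** Item 10 limits "Alanine aminotransferase (ALT) and aspartate aminotransferase (AST") and item 8 limits PT/INR and aPTT. Section 6.2 adds: "Laboratory values (excluding Child Pugh score) on Cycle 1, Day 1 must meet eligibility criteria per Section 3.1".
- **DLT definition (Section 7.1, Table 9).** The general non-hematologic criterion is "≥ grade 3 as per NCI Common Terminology Criteria for Adverse Events (CTCAE) version 5.0". Its listed exceptions cover gastrointestinal events and transient electrolyte abnormalities, not transaminases.
- **On-study hepatic rules (Section 8.1.2).** One rule reads "Subjects who develop acute hepatic toxicity with liver enzymes Grade 3 or higher while on study should be managed per standard dose modification guidelines". Others depend on Child-Pugh class, and INR is one of the five components in Table 12.
- **Lenalidomide rule (Table 13).** It acts on hepatic toxicity of Grade 2 or higher without naming an analyte.

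**The concern.** The primary endpoint of the escalation phase is an MTD fixed by very small DLT counts: 0 of 3 against 1 of 3, or 1 of 6 against 2 of 6. The definition counts a treatment-attributed ALT rise of Grade 3 or higher, but the schedule does not oblige a site to measure ALT while DLTs are being counted. Whether such an event is seen then depends on the local chemistry panel or on an investigator's decision to order the test. The error runs one way: a missed event can turn 1/3 into 0/3 (escalate instead of enrolling three more) or 2/6 into 1/6 (tolerated instead of too toxic).

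There is a smaller reporting consequence. Section 2.4.1 makes the safety profile a primary endpoint, reported as the percentage of patients with each toxicity. If ALT is measured only where local practice includes it, its incidence has no consistent denominator. Separately, an on-study Child-Pugh score computed without INR may come out too low.

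**Working it through.** The plan states no figure to reproduce here: no ALT event rate, no target DLT rate and no operating characteristics for the 3+3 rule. The check sets the lists against the rules and then sizes the consequence under stated assumptions.

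**Step 1. What is required, and when.**

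| Test | Baseline | After Cycle 1 Day 1 |
|---|---|---|
| AST | Section 3.1, Section 6.2, Table 15 | Weekly in cycles 1-2, then Day 1 (Table 15, note b) |
| ALT | Section 3.1, Section 6.2 (not in Table 15) | Not scheduled |
| PT/INR | Section 3.1, Section 6.2 (not in Table 15) | Not scheduled |

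The gap that matters is on treatment.

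**Step 2. Chance of at least one unobserved DLT.** Let q be the per-patient cycle 1 probability of a treatment-attributed ALT rise of Grade 3 or higher with no other DLT, including no qualifying AST rise. Assume that no such event is detected. Then P(at least one in n) = 1 - (1 - q)^n. For example, q = 0.005 gives 1 - 0.995^3 = 0.015 and 1 - 0.995^6 = 0.030.

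**Step 3. Effect on the escalation decision.** Under Section 7.3, dose level 1 or 2 is cleared with 0/3, or with 1/3 followed by 0/3. With total DLT probability p, P(clear) = (1 - p)^3 + 3p(1 - p)^5. Assume that all other DLTs occur at 20%. If ALT-only events go unseen, p = 0.20 and P(clear) = 0.512 + 0.197 = 0.709. If they are counted, p = 0.20 + q. For q = 0.005 this is 0.795^3 + 3(0.205)(0.795^5) = 0.502 + 0.195 = 0.698.

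| Assumed q | At least one missed in 3 | At least one missed in 6 | P(clear), all counted | Excess clearing against 0.709 |
|---|---|---|---|---|
| 0.5% | 1.5% | 3.0% | 0.698 | 1.1 points |
| 1% | 3.0% | 5.9% | 0.687 | 2.2 points |
| 2% | 5.9% | 11.4% | 0.665 | 4.4 points |
| 5% | 14.3% | 26.5% | 0.600 | 10.9 points |

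With other DLTs between 10% and 30%, the excess is 1.7 to 2.2 points at q = 1%, 3.5 to 4.4 at 2%, and 9.2 to 10.9 at 5%.

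**Step 4. Which part of the range is plausible.** Tables 5 and 6 list the most frequent Grade 3 or 4 events above 3% in 1318 monotherapy and 423 combination-therapy subjects. ALT is in neither list. That suggests a rate at or below 3% for any Grade 3 or 4 ALT event over the reported treatment. The rate for cycle 1 events without a matching AST rise should be lower still. The inference is indirect: those pools were other B-cell malignancies, and the combinations did not include lenalidomide.

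**Step 5. Child-Pugh without INR.** Table 12 scores INR from 1 to 3 points, so giving it the minimum understates the total by at most 3 - 1 = 2. Class B can still be reached from scheduled tests: bilirubin 2 + albumin 2 + INR 1 + ascites 1 + encephalopathy 1 = 7. The loss is at the margin: albumin 2 with four components at 1 totals 6 (class A), whereas a true INR score of 2 makes it 7 (class B).

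**The case against.** The strongest reply is that little would escape in practice. AST, bilirubin and alkaline phosphatase are drawn weekly through cycle 1, so a rise that reaches Grade 3 in both transaminases is caught. The protocol's own example is of that kind: "One healthy subject experienced reversible Grade 4 hepatic enzyme increases (AST and ALT) after a dose of 1680 mg". It is one subject at twice the top dose level of 840 mg, and AST rose too, so it is no evidence for isolated ALT events. Section 8.1.2 refers to liver enzymes in general, so AST can trigger that rule, and Section 10.6 requires recording of events found by any clinically significant laboratory test. All of this stands, and it confines the point to AST-discordant ALT rises at sites that do not measure ALT.

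A reader might also infer that ALT and coagulation tests are missing at baseline. The documents do not support that. Section 3.1 sets the limits, Section 3 places screening labs within 7 days before registration, Section 5 has sites verify every criterion, and Section 6.2 reapplies the laboratory limits on Cycle 1 Day 1. Table 15 is not a full list of eligibility tests anyway; the hepatitis PCR in Section 3.2 is not in it.

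What survives is that, during the DLT window, nothing obliges a site to measure an analyte that the DLT definition covers. A primary endpoint based on counts this small should not depend on local panels.

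**Conclusion.** The point holds in a limited form. After Cycle 1 Day 1 neither ALT nor INR is required, while Sections 7.1 and 8.1.2 can turn on them. An ALT-only event of Grade 3 or higher is not required to be observed in the DLT window, and a miss can only favour escalation.

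The size is unknown. Under assumed ALT-only rates of 0.5% to 5%, with none detected, the chance of at least one unobserved DLT is 1.5% to 14.3% in 3 patients and 3.0% to 26.5% in 6. The effect on the decision is smaller: with other DLTs assumed at 20%, about 1 to 11 percentage points of excess clearing. Tables 5 and 6 make the low end more plausible.

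Two stronger readings go too far. One is that these events will go unseen; a site may run ALT in its own panel or order it, so the text supports only that observation is not required. The other is that the Child-Pugh rules cannot operate without INR; a score can be up to 2 points too low, but class B is reachable from scheduled bilirubin and albumin. Confidence is high in the omission and low in any particular size.

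**What to change.** Add ALT to the chemistry group in Table 15 and in Section 9.1.2 at every time point where AST is drawn. It uses the same sample and adds no visit; the cost is a schedule amendment and a few more values to enter.

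Reconcile the schedule with Section 8.1.2 so that an INR is available whenever an on-study Child-Pugh class has to be scored. The timing is for the sponsor to decide. The cost is a coagulation sample at those times.

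Listing the baseline ALT, PT/INR and aPTT in Table 15 would bring it into line with Sections 3.1 and 6.2, but that is tidying only. None of this changes a dose, a hold threshold or the DLT definition.
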